## 1.6 Dose Rationale and Risk/Benefits

Sirolimus will be given as follows: A loading dose of 12mg by mouth will be given on Day 1, and then 4mg by mouth every 24 hours for 9 doses, from Days 2 to 10 inclusive every 28 days if patient is getting consecutively dosed azacitidine, and 11 daily doses Days 2-12 if receiving split doses.

Duration of administration is until disease progression or toxicity requiring discontinuation of the drug.

Azacitidine will be given as follows: 75 mg/m^2/d for 5 consecutive days with two day break and then two additional consecutive days of treatment, i.e. from Day 4-8, 11 and 12 inclusive at least every 28 days. and no longer than 42 days Alternately, azacitidine will be given for 7 consecutive days, day 4-10 inclusive, at least every 28 days and no longer than 42 days.

After 2 cycles (per the current package insert), may increase dose to 100 mg/m^2 if no beneficial effect is seen and no toxicity other than nausea and vomiting has occurred.

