### 3.2.2 Secondary Endpoints

#### 3.2.2.1 Safety and tolerability

- The combination of these drugs will be deemed safe if the number of adverse events is no more than 10% greater than the additive number of events of azacitidine and sirolimus if administrated separately. This will be based upon data in the original phase 2 trials of azacitidine demonstrating an 8% toxic death rate and therefore be 18% of the total number enrolled (approx.  $40 \times 18\% = 7$ ).
- Toxicity will be graded according to the NIH CTC version 4.0 (<http://ctep.cancer.gov/reporting/ctc.html>). Toxicity refers to toxic events during the full course of treatment (through day 21) that are attributed as possibly, probably or definitely due to treatment.

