### **5 Study Drug**

#### **5.1 Sirolimus**

Drug Name: Sirolimus

Other Names: Rapamycin, Rapamune®

Classification: Immunosuppressant Agent

Mode of Action: Rapamycin inhibits T-lymphocyte activation and proliferation in response to antigenic and cytokine stimulation. Its mechanism differs from other immunosuppressants.

Storage and Stability: Store at room temperature, 20°C to 25°C (68°F to 77°F); protect from light.

Dose Specifics: Assigned dose level. Patients will receive a 12mg loading dose of sirolimus. They will then receive a 4mg daily dose of sirolimus beginning 24 hours after the loading dose for the number of days indicated by protocol regimen.

Preparation 1 and 2 mg tablet

Route of Administration: All drug is to be taken by mouth. Doses should be given every 24 hours  $\pm$  2 hours. The drug should be consistently without food. Rapamycin will be given every 24 hours for number of days indicated by protocol regimen.

Incompatibilities: Diltiazem increases serum concentrations of sirolimus. Sirolimus serum concentrations may be increased with use of voriconazole, itraconazole, ketoconazole and fluconazole. Concurrent use of these drugs is contraindicated.

Availability: Available as Rapamune® 1mg tablet and 2mg tablets. Will be available through the Investigational Drug Services.

Side Effects

**Common** (21-100% Frequency) Immediate: Nausea, Vomiting Prompt: Within 2-3 weeks, prior to next course. Diarrhea, Hypertension, Increased creatinine Delayed: Any time after above.

Hypercholesterolemia, Hypertriglyceridemia

**Occasional** (5-20% Frequency) Immediate: Rash Prompt: Within 2-3 weeks, prior to next course.

Infections; edema; weight gain, arthralgia; tremor; acne; myelosuppression; fever; abdominal pain; myalgia; hypokalemia; hypophosphatemia Delayed: Any time after above. Stomatitis

**Rare** (< 5% Frequency) Hepatotoxicity Delayed: Any time after above. Hirsutism, Secondary Lymphoma, Inflammation of the lungs

Nursing/Patient Implications: Monitor blood pressure, and serum creatinine.

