### 5.3 Treatment Regimen

#### 5.3.1 Chemotherapy

- Chemotherapy will consist of a sirolimus 12mg loading dose on day 1 followed by either 9 or 11 consecutive days of administration of sirolimus 4mg. If a split-dose schedule of azacitidine is followed, two additional doses of sirolimus will be given on days 11 and 12 of the 28 day cycles. If the alternate dose schedule is followed, sirolimus will be given on days 1-10. Concurrently, azacitidine 75mg/m^2 will be given on days 4-8, 11 and 12 with cycles repeating every 28 days. Alternately, seven consecutive days of infusion is allowable, i.e. Day 4-10. The schedule, with split dosing or consecutive day dosing, are both frequently used in the outpatient setting given depending on availability of weekend infusion services. Given evidence of near equal efficacy, the decision for consecutive day or split dosing will be decided on the basis of availability of services and the treating physician's discretion. Patients will be offered an option to complete the standard of care chemotherapy treatment at the following Jefferson Health network hospitals: Center City Hospital, Abington Hospital, Aria Hospital, Methodist Hospital and NJ Division (Kennedy) Hospital. All research related procedures are to be done at Jefferson Center City campus. After 2 cycles, may increase dose to 100 mg/m^2 if no beneficial effect is seen and no other toxicity other than nausea and vomiting has occurred.

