### 5.3.2 Dose Reductions

Standard dose reductions for Azacitidine will occur as follows:

If blood counts at time of baseline PD draw WBC  $\geq 3.0 \times 10^9/L$ , ANC  $\geq 1.5 \times 10^9/L$ , and platelets  $\geq 75.0 \times 10^9/L$  adjust the dose as follows, based on nadir counts for any given cycle:

Nadir Counts		% Dose in the Next Course
ANC (<math>\times 10^9/L</math>)	Platelets (<math>\times 10^9/L</math>)	
<0.5	<25.0	50%
0.5 – 1.5	25.0-50.0	67%
>1.5	>50.0	100%

For patients whose baseline counts are WBC  $<3.0 \times 10^9/L$ , ANC  $<1.5 \times 10^9/L$ , or platelets  $<75.0 \times 10^9/L$ , dose reductions will be at the discretion of the treating physician.

At the discretion of the treating physician cycles may be spaced out to up to 42 days apart based upon hematologic response and recovery between cycles.

Renal Toxicity - If unexplained reductions in serum bicarbonate levels to  $<20$  mEq/L occur, the dosage should be reduced by 50% on the next course. If increases in BUN or serum creatinine (unexplained) occur, delay next cycle until values reach baseline or normal, then reduce dose by 50% for next treatment course.

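### The toxicity definition ends at day 21 while treatment repeats in 28- to 42-day cycles, so it is unsettled which later events count in the toxicity summary

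*Combined protocol and SAP*

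**What the plan says.** Section 3.2.2.1 sets the safety endpoint in two bullets. The first gives a limit: the combination is "deemed safe if the number of adverse events is no more than 10% greater" than the sum expected from the two drugs given separately. It is based on earlier azacitidine trials "demonstrating an 8% toxic death rate and therefore be 18% of the total number enrolled", or about 7 of 40. This bullet names no time window.

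The second bullet names the grading scale and defines what counts: "Toxicity refers to toxic events during the full course of treatment (through day 21" (the bracket closes there), restricted to events judged at least possibly related to treatment. It does not say whether day 21 is a study day or a day of each cycle. The list that follows includes marrow aplasia of more than 4 weeks (a second sentence says more than 6), toxicity leading to discontinuation, and death from attributed toxicity.

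On treatment length, Section 1.6 says "Duration of administration is until disease progression or toxicity requiring discontinuation of the drug". Section 5.3.1 has azacitidine "with cycles repeating every 28 days", and Section 5.3.2 adds that "cycles may be spaced out to up to 42 days apart based upon hematologic response" and recovery. Section 1.6 also says "After 2 cycles (per the current package insert), may increase dose to 100" mg/m², subject to conditions.

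Section 8.1 runs adverse event reporting to 30 days after the last dose, and Section 8.2 requires every event in that period to be recorded.

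**The concern.** Safety and tolerability is a stated secondary objective (Section 2.2), and the definition in 3.2.2.1 decides which recorded events are reported as toxicity. A course that continues to progression cannot also end at day 21. Until one half of the definition is chosen, two analysts can produce different toxicity tables from the same data, and the choice could be made after the data are seen.

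The events at risk are not trivial. They include attributed deaths and discontinuations in later cycles, and any toxicity at the increased azacitidine dose. The protocol itself expects some sirolimus effects late. Section 5.1 separates effects seen within 2 to 3 weeks from a later group: "Delayed: Any time after above. Hirsutism, Secondary Lymphoma, Inflammation of the lungs".

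**Working it through.** **The plan's own figure.** 8% + 10 points = 18%, and 0.18 × 40 = 7.2, given as about 7. It reproduces. Nothing in it depends on a time window.

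**Inputs.** Day 21 (3.2.2.1). Cycle length 28 days (5.3.1), up to 42 (5.3.2). Last dosing day of a cycle, 10 or 12, and first azacitidine day, 4 (1.6, 5.3.1). Six cycles as an illustrative horizon, because Section 3.2.2.4 schedules a quality-of-life assessment after six. Six cycles last 6 × 28 = 168 or 6 × 42 = 252 days.

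**Calendar time outside the window, by reading.**

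| Reading of the definition | 28-day cycles | 42-day cycles |
|---|---|---|
| Study day 21, over six cycles | (168 − 21)/168 = 147/168 = 87.5% | (252 − 21)/252 = 231/252 = 91.7% |
| Day 21 of each cycle | 7/28 = 25% | 21/42 = 50% |
| Full course governs | 0% | 0% |

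These are shares of days, not of events, and the first row applies to a patient who completes six cycles.

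**Later cycles.** On the study-day reading all dosing from cycle 2 on falls outside, because cycle 2 starts on day 29 at the earliest.

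**Increased azacitidine dose.** It is allowed after 2 cycles, so the first such dose is on day 4 of cycle 3: study day 2 × 28 + 4 = 60, or 2 × 42 + 4 = 88. On the study-day reading no toxicity at that dose can count.

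**Aplasia criterion.** More than 4 weeks is more than 28 days, and 28 > 21. Even aplasia present on day 1 could not meet the criterion by day 21. The list and the window do not fit together.

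**Comparison with Section 8.1.** That period ends at (k − 1) × 28 + last dosing day + 30 for k 28-day cycles.
- k = 1: 10 + 30 = 40 or 12 + 30 = 42. Day 21 covers 21/42 = 50% to 21/40 = 52.5%.
- k = 6: 140 + 10 + 30 = 180 or 140 + 12 + 30 = 182. Day 21 covers 21/182 = 11.5% to 21/180 = 11.7%.

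The later events are therefore in the database. No section extends the 3.2.2.1 definition to them.

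**The case against.** **The bracket may be a drafting leftover.** The main clause speaks of the whole course, and the aplasia, discontinuation and death items carry no day-21 limit. If the main clause governs, no on-treatment event is lost. This stands as a legitimate third reading. It makes the defect a conflict to resolve, not a demonstrated truncation, but the text does not choose it.

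**Patients are still protected.** This stands in full. Events are recorded to 30 days after the last dose. Events go to the DSMC, with treatment-related deaths due in 24 hours (8.3.2), and Grade 5 events reach the IRB within one working day (8.3.1.3).

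**A stronger inference that should not be drawn.** A reader might conclude that the combination could pass the 7-of-40 limit through under-counting. Suppose a true toxic-death rate of 25% over six 28-day cycles at constant hazard. The share captured by day 21 is 1 − 0.75^(21/168) = 0.035, and the binomial chance of more than 7 in 40 falls from 0.82 to below 0.001. The documents do not support this, for three reasons:
- The limit is in a separate bullet, is worded as adverse events, and names no window. It may well follow Section 8.1, in which case it loses nothing.
- The 25% has no source. The documents give 8% (3.2.2.1) and, for infectious deaths with sirolimus-MEC, 7.5% overall and 6% at the planned dose (1.6). At 6% to 8% the chance of more than 7 in 40 is only 0.002 to 0.013 with full counting.
- The day-21 figure is fragile. Keep 25%, put half the deaths in cycle 1, and date events by onset with death 14 or 28 days later. The captured share is then 0.125 + 0.125 × 7/140 = 0.131 or 0.125 + 0.125 × 21/140 = 0.144, and the chance becomes 0.15 or 0.21.

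**The benchmark's own window is unknown.** This also stands. If the 8% came from a shorter observation period, a longer trial window makes the comparison less like-for-like.

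**Conclusion.** The definition contradicts the treatment schedule and its own aplasia criterion, and should be corrected before the toxicity summary is produced. The possible loss ranges from nothing (full course governs), through the last 7 to 21 days of each cycle, to everything from cycle 2 on (study day 21). The percentages rest only on the stated cycle lengths and the six-cycle horizon.

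The effect is confined to which recorded events are summarised as toxicity. Data capture, safety reporting and the primary response analysis are untouched. Whether the 7-of-40 limit is affected cannot be determined from the text, so no error rate for a safe verdict should be quoted. The conflict itself is certain. Its practical consequence depends on a reading that the documents leave open.

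**What to change.** For analysis and reporting only:
- Delete the day-21 bracket from the endpoint definition. State that attributed toxicity is counted in all cycles, from first dose to 30 days after the last administration, which is the existing end of follow-up in Section 8.1. Keep the attribution rule.
- State that the limit in 3.2.2.1 uses the same window, and note beside the comparison that the window behind the 8% benchmark is not given.

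Two matters are for the sponsor to reconcile, and no clinical rule is proposed here. Section 4.4.1 refers to 3.2.2.1 for unacceptable toxicity as a reason to stop treatment, so the analysis window should be stated separately and not change that use by side effect. The aplasia durations also differ: more than 4 and more than 6 weeks in 3.2.2.1, more than 4 weeks in 8.3.2.

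Cost: no new data, since events and their relatedness are already recorded under Sections 8.1 to 8.2.1. The change restates a safety endpoint after Arms B and C closed with 27 and 7 patients, so it needs a dated amendment and one re-tabulation covering all arms. Reported counts would be higher than under either day-21 reading wherever attributed toxicity occurred after the cut-off.

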#### ***The following will be considered toxicities***

- Non-hematologic toxicity is defined as Any Grade III or Grade IV non-hematologic toxicity attributable to the investigational drug with the specific exclusion of:
  - a. Grade III nausea and vomiting responsive primarily to non-parenteral anti-emetics, intermittent use of parenteral anti-emetics is acceptable.
  - b. Grade III fever or infection
  - c. Splenic Infarction
  - d. Grade III/IV Tumor lysis syndrome
  - e. Grade III/IV metabolic abnormalities attributable to anti-fungal medication or tumor lysis syndrome that is correctable with IV or PO supplementation.
  - f. Grade III/IV stomatitis that resolves within 14 days of neutrophil recovery
  - g. Grade III/IV hypercholesterolemia / hypertriglyceridemia
  - h. Grade III hyperbilirubinemia and/or transaminitis that resolves to less than or equal to a grade II toxicity within 14 days.

Hematologic toxicity: Marrow aplasia (defined as <10% cellularity with <10% blast) > 4 weeks not attributable to disease. All unanticipated > Grade 2 non-hematologic AE's will be reported. The only hematologic event which will be considered an AE/SAE for this study is marrow aplasia (defined as <10% cellularity with <10% blast) > 6 weeks not attributable to disease and this will be reported. There is no degree of neutropenia, anemia, or thrombocytopenia that would qualify as an AE/SAE as the purpose of the treatment is to create a period of complete aplasia in the marrow.

- Blood product transfusion will not be considered a limiting toxicity, since these patients require frequent transfusions secondary to disease process.
- Toxicity requiring discontinuation of therapy or removal of the patient from the study.
- Death resulting from toxicity attributed to the combination of sirolimus and azacitidine.

#### 3.2.2.2 Pharmacokinetic assessment

Pharmacokinetic assessment at Day 4 will assess levels of the drug in vivo. The Day 4 levels will be drawn prior to initiation of azacitidine to allow for a PK/PD correlation study. No dose adjustment is planned on the basis of these studies.

#### 3.2.2.3 Pharmacodynamic assessment

The secondary pharmacodynamic endpoint is to determine if rapamycin effectively inhibits mTOR signaling at levels achieved in this regimen.

We want to define in vivo, the percentage of baseline samples that have activation of the S6 ribosomal protein and the percentage of those that were found to be activated which are subsequently inhibited by sirolimus in the post treatment sample. [S6 positive blasts post-treatment minus % S6 positive blasts at baseline]

We will determine the ability of oral sirolimus to inhibit mTOR in leukemic blasts. This will be measured by intracellular flow cytometry for phosphorylation of the downstream signaling target S6 ribosomal protein as a surrogate for mTOR activity. Flow results will be confirmed by Western blot as appropriate. The in vivo effects of sirolimus will be compared to a whole blood *ex vivo* rapamycin dose response curve for each sample as well as to sirolimus levels obtained at the time of pharmacodynamic measurements. Finally, S6 inhibition will be correlated with clinical outcome. We will draw PD datapoints on day 1 before treatment, Day 4 before azacitidine administration. If patient have less than 5000/ $\mu$ l of blasts in the periphery, than a bone marrow aspirate will be performed for analysis.

We hypothesize that oral sirolimus will fully inhibit S6 in sampled leukemic blasts if concentrations exceed a threshold established by *ex-vivo* rapamycin therapy of the baseline sample. We will therefore expose this sample to increasing doses of rapamycin *ex vivo* and then measure mTOR activation by flow cytometry.

### 3.2.2.4 Quality of Life assessment

To determine if patient's quality of life is improved while on this combination regimen, we will ask patients to complete two, previously validated instruments designed to assess physical symptoms and functioning, psychological state, social functioning, and demographic characteristics. The European Organization for Research and Treatment of Cancer (EORTC) QOL and the Mental Health Inventory (MHI) will be administered prior to treatment on day 1, on day 84 (after three cycles), and on day 164 (after six cycles)  $\pm$  30 days.

## 4 Subject Selection and Withdrawal

### 4.1 Inclusion Criteria

1. Patients must have a diagnosis of one of the following:
  - MDS (Arm A)
    - i. High-risk MDS defined as: >5% blasts in bone marrow and/or the following cytogenetic categories: presence of inv(3)/t(3q)/del(3q), -7/del(7q), complex cytogenetics (3 or more abnormalities)
  - AML (Arm B)
    - i. Relapsed/refractory/unable to tolerate conventional chemotherapy
  - MDS or AML clinical diagnosis with prior therapy with azacitidine (Arm C)
- \*Note: As of July 2018, only high-risk MDS patients will be eligible as Arm B is closed. As of October 2017, those patients with MDS who have received prior treatment will now be enrolled on Arm A as Arm C is closed.
2. Patients must be  $\geq$  18 years old
3. Patients must have an ECOG performance status of  $\leq$  2 (see Attachment 1).
4. Patients must have a life expectancy of at least 4 weeks.
5. Patients must be able to consume oral medication.
6. Patients must have completed any radiotherapy four weeks prior to study entry, 0-2 weeks for local palliative XRT (small port).
7. Patients must have recovered from the toxic effects of any prior chemotherapy to < Grade 2 (except for alopecia).
8. Required initial laboratory values: Creatinine  $\leq$  2.0mg/dL; total or direct bilirubin  $\leq$  1.5mg/dL (if not due to the leukemia itself or known Gilbert's Syndrome); (as documented by treating physician) SGPT (ALT)  $\leq$  3xULN; glucose <200 mg/dL, negative pregnancy test for women of child-bearing potential.
9. Patients must be able to sign consent and be willing and able to comply with scheduled visits, treatment plan and laboratory testing.
10. Patients may have had a prior stem cell transplant (autologous or allogeneic), however they may not have active GvHD, nor be on any immunosuppression

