## Study Summary

Title	A Phase II Study of Azacitidine and Sirolimus for the Treatment of High-risk MDS and Patients with Acute Myeloid Leukemia Refractory To or Not Eligible for Intensive Chemotherapy.
Short Title	Sirolimus/Azacitidine
Phase	II
Methodology	Open label
Accrual Duration	83 months
Study Center(s)	1. Jefferson Health Network (Center City Hospital, Abington Hospital, Aria Hospital, Methodist Hospital and NJ Division (Kennedy) Hospital
Objectives	This is a study to determine estimate of efficacy of sirolimus when administered with azacitidine.  Secondary objectives are to determine the pharmacodynamic effect of rapamycin on inhibition of mTOR and the safety of the combination of the regimen.
Number of Subjects	74;
Diagnosis and Main Inclusion Criteria	

Adults with high-risk MDS or relapsed or refractory AML or those unable or unwilling to tolerate high dose chemotherapy.

Age <math>\geq 18</math>

Study Product, Dose, Route, Regimen	Sirolimus loading dose of 12mg on day 1 followed by a single daily dose of 4 mg/ day on days 2 through 10 or 12  Azacitidine 75 mg/m  /d for 5 consecutive days, two days rest, then two consecutive days every 28 days or: Azacitidine 75 mg/m  /d for 7 consecutive days. After 2 cycles, may increase dose to 100 mg/m 
Duration of administration	Until disease progression or toxicity requiring discontinuation of the drug
Reference therapy	Fenaux et al. J ClinOncol. 2010 Feb 1;28(4):562-9.
Statistical Methodology	This study is a phase II trial. The study will be stratified to arms A, B, and C. Arm A (high risk MDS) will need 40 patients total for an optimal Simon 2-stage design (with alpha=0.1 and 80% power) with 23% standard response rate vs. an expected 40% response rate. Arm B (AML) We will need 43 patients total for an optimal Simon 2-stage design (with alpha=0.05 and 80% power) with 20% standard response rate vs. an expected 40% response rate. Arm C (either MDS or AML with prior Azacitidine therapy) will need 29 patients total for an optimal Simon 2 stage design (with alpha = 0.05 and 80% power) with a 5% response rate versus a 20% response rate.

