### 4.2 Exclusion Criteria

1. Patients must not be currently receiving any chemotherapy agents (except Hydroxyurea)
  - a. Intrathecal ARA-C and intrathecal methotrexate are permissible (as they are not systemic and only isolated to the central nervous system).

- b. Patients cannot have received more than 3 prior lines of therapy for their hematologic malignancy. Patient may have previously had azacitidine or decitabine will be eligible to enroll on Arm A (MDS).
2. Patients must not be receiving growth factors.
3. Patients with a current second malignancy requiring systemic therapy, other than non-melanoma skin cancers, are not eligible. If a patient has had a prior second malignancy that is not currently requiring active treatment, the patient will be considered eligible.
4. Patients with uncontrolled high blood pressure, unstable angina, symptomatic congestive heart failure, myocardial infarction within the past 6 months or serious uncontrolled cardiac arrhythmia are not eligible.
5. Patients may not take any of the following medications while on study, but will be considered eligible if medication is discontinued 72 hours prior to first dose of Sirolimus:
  - Carbamazepine (e.g. Tegretol)
  - Rifabutin (e.g. Mycobutin)
  - Rifampin (e.g. Rifadin)
  - Rifapentine (e.g. Priftin)
  - St. John's Wort- may decrease effects of sirolimus by decreasing the amount of sirolimus in the body
  - Clarithromycin (e.g. Biaxin)
  - Cyclosporin e.g. (Neorla or Sandimmune)
  - Diltiazem (e.g. Cardizem)
  - Erythromycin (e.g. Akne-Mycin, Ery-Tab)
  - Itraconazole (e.g. Sporonox)
  - Fluconazole (e.g. Diflucan)
  - Ketoconazole (e.g. Nizoral)
  - Telithromycin (e.g. Ketek)
  - Verapamil (e.g. Calan SR, Isoptin, Verelan)
  - Voriconazole (e.g. VFEND) - May increase the effects of sirolimus by increasing the amount of this medicine in the body. Can take 72 hours after last dose of Sirolimus
  - Tacrolimus (e.g. Prograf) – May cause liver transplant rejection or serious side effects in patients on sirolimus.
6. Patients with known HIV positivity or AIDS-related illness are not eligible.
7. Patients with other severe concurrent disease which in the judgment of the investigator would make the patient inappropriate for entry into this study are ineligible.
8. Patients must not have received any investigational agents within 21 days of study entry.

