### 5.3.5 Method for Assigning Subjects to Treatment Groups

This is an open label study of a single therapy regimen.

Once eligibility has been established and confirmed by signature of the Jefferson principal investigator, the Research Coordinator at TJU will then be assigned a registration number according to the subject's diagnosis (MDS or refractory AML). This number is unique to the participant on this trial and must be used moving forward (i.e. for CRF completion, SAE reporting, etc). As of October 2017 and July 2018, both Arm C and Arm B are closed to enrollment respectively. Patients with MDS who have received prior treatment will be allowed to enroll onto Arm A.

A master study enrollment log will be maintained by the study team at the Thomas Jefferson University.

Patients cannot be registered to this study on the weekends. The [name] lab at UPenn cannot accept samples after 1pm.

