## 7 Statistical Plan

### 7.1 Sample Size and Study Duration

This study is considered a phase II study.

For the MDS Arm A:

The optimal two-stage design to test the null hypothesis that  $P \leq 0.230$  versus the alternative that  $P \geq 0.400$  has an expected sample size of 24.60 and a probability of early termination of 0.592. If the drug is actually not effective, there is a 0.090 probability of concluding that it is (the target for this value was 0.100). If the drug is actually effective, there is a 0.200 probability of concluding that it is not (the target for this value was 0.200). After testing the drug on 14 patients in the first stage, the trial will be terminated if 3 or fewer respond. If the trial goes on to the second stage, a total of **40 patients** will be studied. If the total number responding is less than or equal to 12, the drug is rejected.

For the AML Arm B:

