**Note: As of July 2018, Arm B was closed after accruing 27 patients.**

The optimal two-stage design to test the null hypothesis that  $P \leq 0.200$  versus the alternative that  $P \geq 0.400$  has an expected sample size of 20.58 and a probability of early termination of 0.747. If the drug is actually not effective, there is a 0.050 probability of concluding that it is (the target for this value was 0.050). If the drug is actually effective, there is a 0.200 probability of concluding that it is not (the target for this value was 0.200). After testing the drug on 13 patients in the first stage, the trial will be terminated if 3 or fewer respond. If the trial goes on to the second stage, a total of **43 patients** will be studied. If the total number responding is less than or equal to 12, the drug is rejected.

For the pre treated Arm C:

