**Note: As of October 2017, Arm C was closed after accruing 7 patients.**

The optimal two stage design to test the null hypothesis that  $P \leq 0.05$  versus the alternative that  $\geq 0.200$  has an expected samples size of 10 and a probability of early termination of 0.508. If the drug is actually not effective, there is a 0.050 probability of concluding that it is (the target for this value was 0.050). If the drug is actually effective, there is a 0.200 probability of concluding that it is not (the target of this value was 0.200). After testing the drug on 10 patients in the first stage, the trial will be terminated if zero patients respond. If the trial goes on the second stage, a total of **29 patients** will be studied. If the total number responding is less than or equal to 3, the drug is rejected.

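### Arm A has taken previously treated MDS patients since October 2017, but section 7.1 still gives one 23% vs 40% design at 80% power, and 7.2 has no analysis by prior exposure

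*Combined protocol and SAP*

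**What the plan says.** Three places move the population. Section 4.1 states that "those patients with MDS who have received prior treatment will now be enrolled on Arm A as Arm C is closed". Section 4.2 makes MDS patients with earlier azacitidine or decitabine eligible for Arm A, subject to a general limit: "Patients cannot have received more than 3 prior lines of therapy for their hematologic malignancy". Section 5.3.5 repeats the rule: "Patients with MDS who have received prior treatment will be allowed to enroll onto Arm A".

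Before this, MDS or AML with prior azacitidine had its own arm, introduced in 7.1 as "For the pre treated Arm C". The Study Summary designed that arm "with a 5% response rate versus a 20% response rate". Section 7.1 then notes: "As of October 2017, Arm C was closed after accruing 7 patients".

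For Arm A, section 7.1 gives a null of 23%, a target of 40%, alpha 0.090 and a type II error of 0.200. Of the first stage it says "After testing the drug on 14 patients in the first stage, the trial will be terminated if 3 or fewer respond", and the drug is rejected at 12 or fewer responses among 40. This text does not mention the change in population. The Study Summary's total of 74 equals 40 + 27 + 7, so Arm A's 40 was kept after the other two arms closed. Section 7.2 describes no analysis by prior exposure.

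**The concern.** The plan once judged prior azacitidine important enough to need a separate arm with a much lower null and target. Its own background agrees: section 1.1 reports poor survival after progression through hypomethylating agents, and worse results in previously treated patients in an AML azacitidine series. Some of these patients now count towards Arm A's response total, with no change to the benchmarks.

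Arm A is the only arm still open, and response is the primary endpoint. If pretreated patients respond less often, a combination that meets the plan's hopes in each group is rejected more often than the stated 20%. The pooled rate also loses its reference. With 10 of 40 pretreated and Arm C's rates as a proxy, the null for the mix is 18.5% and the target 35.0%, not 23% and 40%. Section 7.2 promises baseline summaries, which could show the mix, but nothing would show response by prior exposure.

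**Working it through.** **Inputs.** From 7.1: stage 1 of 14, stop at 3 or fewer; total 40, reject at 12 or fewer; 23% vs 40%. From the Study Summary and 7.1 (Arm C): 5% vs 20%, used here as a proxy for pretreated patients. Not in the documents: the number M pretreated on Arm A, and how far Arm A had accrued by October 2017. M = 2, 4, 6 and 10 are therefore illustrations.

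**Formula.** Let X1 be responses among the first 14 and X2 responses among the next 26. Success is X1 ≥ 4 and X1 + X2 ≥ 13, so

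P(success) = Σ over x = 4 to 14 of P(X1 = x) · P(X2 ≥ 13 − x).

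With m pretreated patients in a stage of size n, the stage count is the sum of independent Binomial(n − m, p of the others) and Binomial(m, p of the pretreated).

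**Reproducing 7.1 (M = 0).**
- At 23%: P(X1 ≤ 3) = 0.592; expected size = 14 + (1 − 0.5924) × 26 = 24.60; alpha = 0.0904.
- At 40%: power = 0.8000.

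All four agree with the stated 0.592, 24.60, 0.090 and 0.800.

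**Mixed arm.** The figures average over the hypergeometric split of M pretreated patients between 14 stage 1 places and 26 stage 2 places. Patients not pretreated are at 23% (null) or 40% (target). The pooled columns use the proxy rates.

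| Pretreated of 40 | Pooled null | Pooled target | Alpha (23%/5%) | Power (40%/20%) | Power (40%/30%) |
|---|---|---|---|---|---|
| 0 | 23.0% | 40.0% | 0.090 | 0.800 | 0.800 |
| 2 | 22.1% | 39.0% | 0.069 | 0.769 | 0.785 |
| 4 | 21.2% | 38.0% | 0.051 | 0.734 | 0.768 |
| 6 | 20.3% | 37.0% | 0.037 | 0.695 | 0.751 |
| 10 | 18.5% | 35.0% | 0.017 | 0.609 | 0.714 |

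Pooled rates at 10/40: (30 × 0.23 + 10 × 0.05)/40 = 0.185 and (30 × 0.40 + 10 × 0.20)/40 = 0.350. If pretreated patients also respond at 40%, power is 0.800 in every row.

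**Stage.** Placement matters because of the early stop. With 40%/20%, the chance of stopping at stage 1 is 0.124, 0.172 and 0.232 with 0, 2 and 4 pretreated among the first 14. At 4/40, power is 0.681 if all four fall in stage 1 and 0.756 if all fall in stage 2. At 6/40 the limits are 0.606 and 0.727.

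**The case against.** The strongest reply is that section 7.1 contains no error. Its type II error is stated for a response rate of at least 40% and is right on that condition. That stands: nothing here shows a miscalculated design.

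Second, the loss depends on a proxy. Arm C's rates covered MDS or AML after azacitidine. Arm A now takes MDS after undefined prior treatment, and no rate is given for decitabine or for other treatment. Section 1.1 also hopes that sirolimus may rescue response in patients already given azacitidine. This limits the size of the loss, which is why the 30% and 40% cases are shown. It does not remove the point: the plan gives that hope as part of its rationale, yet set 20% and not 40% for prior-azacitidine patients.

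Third, the number pretreated may be small. Arm C enrolled only 7 patients, MDS and AML together, so 10 pretreated MDS patients on Arm A would exceed its whole accrual. This is fair, and the 2/40 and 4/40 rows deserve as much weight as the others.

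Two stronger readings are tempting. A reader might infer that Arm A's power is now about 61%; the documents do not support any single figure, since neither the number pretreated nor their response rate is known. A reader might also infer that mixing populations inflates the false-positive rate; under the plan's own null rates it lowers it.

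**Conclusion.** The point stands as a gap between who may enrol on Arm A and what sections 7.1 and 7.2 assume. The omission is certain: eligibility changed, while the Arm A benchmarks, power statement and analysis text did not. The size is conditional. With a 20% pretreated target, 40% for the others and random placement across stages, power falls from 0.800 to between 0.769 (2/40) and 0.609 (10/40). With a 30% target the range is 0.785 to 0.714, and with 40% there is no loss. Under nulls of 23% and 5%, alpha falls to between 0.069 and 0.017, so type I error is not breached. The harm is a possible false negative and a pooled rate that cannot be compared with 23%. It should be fixed, but it does not invalidate the decision rule.

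**What to change.** In 7.1 and 7.2:

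1. State that Arm A has included pretreated MDS since October 2017, and define prior treatment. Replace the unconditional 80% with a short table of alpha and power by number pretreated. Name the assumed pretreated rates and include the 30% sensitivity. Insert actual numbers, by stage, once known.
2. Keep the pooled 3/14 then 12/40 as the only decision rule. Report response rates with exact 95% confidence intervals separately for hypomethylating-agent-naive and pretreated patients, labelled descriptive. Confirm that prior hypomethylating therapy is recorded: section 5.6 speaks of cytotoxic regimens, while 5.2 classes azacitidine as a hypomethylating agent. This may already be covered, since 5.3.1 lists azacitidine under chemotherapy and prior lines are checked at entry.

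A separate pass mark for naive patients is best avoided. Suppose success could be claimed on either reading, with all pretreated patients in stage 2, a 23% null for everyone, and the naive cutoff set as the smallest with alpha at most 0.10. The overall type I error would then be 0.119 with 7 pretreated (naive n = 33, reject at 10 or fewer) and 0.123 with 11, above the 0.10 target.

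The cost is text and one table, with no extra patients; at most one data field, or a chart check, is added. The downside is a less favourable stated power and imprecise subgroup estimates: 2 responses in 10 has an exact 95% interval of 2.5% to 55.6%. The gain is in interpretation; power does not rise.
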